5.6. Pharmacodynamic and Biomarker Variables

Pharmacodynamic and biomarker variables are:

Serum Total IgE: Serum total IgE is a marker of Type 2 activity. Dupilumab significantly suppressed total IgE in studies of adult AD, nasal polyposis, and asthma patients.

Serum Peanut-Specific Antibody Assays (IgE, IgG, IgG4 against peanut extract and peanut protein allergen components): The induction of peanut allergen specific IgG4 during OIT has been reported in multiple studies. In a 5-year peanut OIT study of 39 peanut-allergic children, increases in total peanut-specific IgG levels were reported during the 12-month up-dosing period (Vickery 2014). In an open-label study of 29 peanut-allergic children, peanut-specific IgG4 increased steadily during the first year of treatment, reaching 3.5-fold increase over baseline after 3 months of OIT and roughly 10-fold increase at the end of first year (Jones 2009). In the same study, peanut allergen specific IgE was seen to increase by ~3-fold after 3 months of OIT and gradually return to baseline at one year.

In study R668-AD-1307 and other dupilumab studies in adults, dupilumab suppressed both total and allergen-specific IgEs. In general, dupilumab suppresses total IgE by \sim 50% with 12 to 16 weeks of treatment.

Regeneron Pharmaceuticals, Inc.

CONFIDENTIAL

Page 42 of 118

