5. STATISTICAL METHODS

For continuous variables, descriptive statistics will include the following: the number of subjects reflected in the calculation (n), mean, standard deviation, median, first quartile (Q1), third quartile (Q3), minimum, and maximum.

For categorical or ordinal data, frequencies and percentages will be displayed for each category.

All data will be summarized by the following treatment groups in each period:

- 1. Double-blind treatment period before dosing with AR101 (4 weeks)
 - Dupilumab
 - Placebo
- 2. Double-blind treatment period with up-dosing of AR101 (24 to 36 weeks):
 - Dupilumab + AR101
 - Placebo + AR101
- 3. Double-blind maintenance period of AR101 (24 weeks):
 - Continuously on placebo+ AR101
 - Previously on dupilumab + AR101 and re-randomized to placebo + AR101 (dupilumab + AR101/placebo + AR101)
 - Continuously on dupilumab + AR101

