5.11. Analysis of Biomarker Data

All biomarker analyses will be performed on the mFAS and FAS-maintenance using all observed data. Descriptive statistics for the observed values, change from baseline and percent change from baseline values by treatment and visit will be provided for the biomarker variables as described in Section 4.9.

The Wilcoxon signed-rank test will be used to test if the change or percentage change from baseline value is significantly different from zero. P-value will be reported.

For up-dosing period, exploratory analyses for the difference between dupilumab + AR101 group and placebo + AR101 group on the change from baseline and percent change from baseline values will be performed using a rank-based ANCOVA model with treatment group and randomization stratification factors as fixed factors, and the relevant baseline values as covariate. Missing value will be imputed by LOCF method using available post-baseline data for visits up to visit 16. Pvalue for difference between dupilumab +AR101 and placebo + AR101 will be provided.

For maintenance period, exploratory analyses for the difference between continuously on dupilumab + AR101 group and continuously on placebo + AR101 group on the change from baseline and percent change from baseline values will be performed using a rank-based ANCOVA model with treatment group and randomization stratification factors as fixed factors, and the relevant baseline values as covariate. Missing value will be imputed by LOCF method using available post-baseline data for visits up to visit 22. P-value for difference between continuously on dupilumab + AR101 and continuously on placebo + AR101 will be provided.

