Correlation of baseline serum peanut sIgE, sIgG, sIgG4, total IgE, absolute change or percent change at visit 16, 22 and 25 from baseline in these biomarkers; baseline Ara h1 sIgE, Ara h1 sIgG4, Ara h2 sIgE, Ara h2 sIgG4, Ara h3 sIgE, Ara h3 sIgG4, absolute change or percent change at visit 16 in these biomarkers; baseline in basophil sensitivity to peanut allergen stimulation measured by EC50, frequency of peanut specific T-cell subsets (e.g. Th2A cells), and absolute change or percent change at visit 16 in these biomarkers with the following continuous clinical endpoints will be explored using the Spearman's rho test. Both Spearman correlation coefficients and p-value will be reported. The correlation between post-baseline biomarkers and clinical outcomes will only be evaluated at the same visit.

- Change in the cumulative tolerated dose (log transformed) of peanut protein during a DBPCFC from baseline to visit 16 in subjects treated with dupilumab plus AR101 vs placebo plus AR101
- Change in the cumulative tolerated dose (log transformed) of peanut protein during a DBPCFC from baseline to visit 22 in subjects (continuously) treated with dupilumab plus AR101 vs placebo plus AR101
- Change in the cumulative tolerated dose (log transformed) of peanut protein during a DBPCFC from baseline to visit 25 in subjects (continuously) treated with dupilumab plus AR101 vs placebo plus AR101
- Change in the normalized wheal size of titrated skin prick test from baseline to visit 16 in subjects treated with dupilumab plus AR101 vs placebo plus AR101
- Change in the normalized wheal size of titrated skin prick test from baseline to visit 22 in subjects (continuously) treated with dupilumab plus AR101 vs placebo plus AR101
- Change in the normalized wheal size of titrated skin prick test from baseline to visit 25 in subjects (continuously) treated with dupilumab plus AR101 vs placebo plus AR101
- Change in the FeNO from baseline to visit 16 in subjects treated with dupilumab plus AR101 vs placebo plus AR101
- Change in the FeNO from baseline to visit 22 in subjects (continuously) treated with dupilumab plus AR101 vs placebo plus AR101
- Change in the FeNO from baseline to visit 25 in subjects (continuously) treated with dupilumab plus AR101 vs placebo plus AR101

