Correlation of baseline serum peanut sIgE, sIgG, sIgG4, total IgE, basophil sensitivity to peanut allergen stimulation, and Th2A cell frequency with the following binary clinical endpoints will also be explored using logistic model. The model will include the responder/non-responder of below clinical endpoint as the dependent variable, with randomization stratification factors, treatment group, baseline biomarker value, and treatment by baseline biomarker interaction as the predictor variables. Model coefficients and P-value will be provided to indicate significance of the correlation/association.

• Subjects treated with dupilumab plus AR101 vs placebo plus AR101 who "pass" 2044 mg (cumulative) peanut protein at visit 16

- Subjects treated with dupilumab plus AR101 vs placebo plus AR101 who "pass" 1044 mg (cumulative) peanut protein at visit 16
- Subjects treated with dupilumab plus AR101 vs placebo plus AR101 who "pass" 444 mg (cumulative) peanut protein at visit 16

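### SAP 5.11 correlates biomarker change with clinical change without treatment adjustment or a within-arm statement; run on both arms together, the correlation can arise from treatment alone

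*SAP*

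**What the plan says.** SAP 5.11 lists baseline values and post-baseline changes in peanut-specific IgE, IgG and IgG4, total IgE, Ara h component antibodies, basophil EC50 and T-cell subsets. It sets them against continuous clinical endpoints: change in log tolerated dose, in titrated skin-prick wheal size and in FeNO. The associations "will be explored using the Spearman's rho test. Both Spearman correlation coefficients and p-value will be reported". Timing is fixed: "The correlation between post-baseline biomarkers and clinical outcomes will only be evaluated at the same visit". The visit 16 endpoints are described as changes "from baseline to visit 16 in subjects treated with dupilumab plus AR101 vs placebo plus AR101", and the visit 22 and 25 endpoints likewise name continuously treated dupilumab subjects and placebo subjects together. The population is set at the head of the section: "All biomarker analyses will be performed on the mFAS and FAS-maintenance using all observed data".

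Treatment appears in the analyses on either side. The rank-based ANCOVA of biomarker change earlier in 5.11 has treatment group as a factor. The logistic analysis that closes the section is fitted "with randomization stratification factors, treatment group, baseline biomarker value, and treatment by baseline biomarker interaction as the predictor variables". Only the Spearman paragraph between them is silent on treatment.

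**The concern.** Both members of each pair are measured after randomization, and the sponsor expects treatment to move both. Protocol 5.6 says that in earlier adult studies "dupilumab suppressed both total and allergen-specific IgEs", and it hypothesizes that FeNO will fall under dupilumab in these children. The sample-size section plans for pass rates of 65% against 40%. If dupilumab lowers a marker and raises tolerated dose, dupilumab subjects cluster at low marker and high dose, and placebo subjects at the opposite corner. Ranking everyone together then gives a negative rho even if, among subjects on the same treatment, the marker says nothing about who tolerates more peanut. The p-value could be read as evidence that biomarker response tracks desensitization when it only restates the treatment effect. That reading is most likely if the trial succeeds.

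**Working it through.** **The plan's own figure.** The SAP gives no number for the correlation analysis, so the check starts from its sample-size inputs: 40% and 65% pass rates, 52 and 104 subjects, two-sided 5% Fisher exact test. Full enumeration gives 81.1% power against the stated 80%, so those inputs are reproduced and can be used below.

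**Inputs.** The mFAS is about 122 (SAP 2.3), taken as 81 dupilumab and 41 placebo at 2:1. Pass rates are 65% and 40%. Within-arm association is set to zero. Assumed, because no SDs are given: the marker shift d in within-arm SD units, and the spread of tolerated doses below a pass.

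**Step 1: size of the induced correlation.** For two variables independent within arm and shifted by d1 and d2 SDs, with share p on dupilumab, the pooled correlation has magnitude

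r = p(1-p)·d1·d2 / sqrt{[1 + p(1-p)·d1²]·[1 + p(1-p)·d2²]}.

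Here p = 81/122 = 0.664 and p(1-p) = 0.223.

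- d1 = 1.0, d2 = 0.5: r = 0.1116 / sqrt(1.223 × 1.056) = 0.10.
- d1 = 1.5, d2 = 0.8: r = 0.2678 / sqrt(1.502 × 1.143) = 0.20.

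The approximate test statistic is atanh(r)·sqrt(122 - 3). This gives 1.07 and 2.26, so rejection near 19% and 62%. Simulation of Spearman's rho (3,000 trials per setting, normal variables) gave 18% and 62%. Shifts of 0.5 and 0.5 SD gave 8%, and 1.0 and 0.8 SD gave 39%. Across all six settings mean rho ran from -0.05 to -0.21. Within the dupilumab arm alone rejection was 5.0% to 5.6%.

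**Step 2: tolerated dose at the plan's effect.** Tolerated dose was simulated as five ordered levels whose top level has probability 40% on placebo and 65% on dupilumab. On a normal scale that is a shift of 0.385 + 0.253 = 0.64 SD, inside the 0.5 to 0.8 range of step 1. The placebo share in the lowest level was varied over 10%, 20% and 40%; ranges in the table cover all three (3,000 trials each).

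| Marker shift d (SD) | Mean pooled rho | Pooled p<0.05 | Treatment-adjusted p<0.05 |
|---|---|---|---|
| 0 | 0.00 | 5% | 5% |
| 0.5 | -0.06 | 9-10% | 4-5% |
| 1 | -0.11 | 22-24% | 4-5% |
| 1.5 | -0.15 | 36-39% | 4-5% |
| 2 | -0.18 | 50-54% | 5% |
| 3 | -0.20 to -0.21 | 61-65% | 4-5% |

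The adjusted version removes arm means from the ranks before correlating. Its mean rho is about 0.00 throughout.

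**Step 3: what drives it.** At d = 2 with equal 50% pass rates, pooled rho is 0.00 and rejection 5%: a marker effect alone is not enough. With 40% against 80% it is -0.29 and 92%. With 40 per arm at the planned pass rates (an assumed stand-in for the more even visit 22 split) it is -0.20 and 43%. For a continuous outcome such as wheal size or FeNO shifted by an assumed 1 SD (2,000 trials), the magnitude of rho is 0.18 with 51% rejection at d = 1, and 0.29 with 92% at d = 2.

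**The case against.** The strongest reply is that the SAP never says the arms are combined. The both-arms wording repeats the endpoint labels of SAP 4.5.2, where it names a comparison, and section 5 has a general rule: "All data will be summarized by the following treatment groups in each period". This stands to the extent that pooling is an inference. But that rule governs summaries and does not say how a correlation with a p-value is run. Neighbouring text states treatment where it is wanted.

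A second reply is that the shifts are not from the documents. Protocol 5.6 gives no SD, its suppression data come from adults, and it also cites about a 3-fold rise in peanut-specific IgE after 3 months of immunotherapy, returning to baseline by one year. Basophil and T-cell samples are optional, so n is smaller there. All of this is fair, and it is why a range is shown.

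Third, the contrast with the logistic model is not like for like, since that model uses baseline markers only. That is correct. The closer comparison is the rank-based ANCOVA, which analyses change and includes treatment.

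Fourth, if dupilumab works through IgE, part of the overall association is mediated by treatment, and adjustment removes it. An overall rho is then a legitimate descriptive quantity. This also stands, so a ban on the pooled value is not justified.

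Finally, the analysis is exploratory, and readers will see the treatment shift in the by-treatment biomarker tables. That limits the harm but does not make an unadjusted p-value interpretable.

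**Conclusion.** The point holds as a gap in specification with a foreseeable bias if the natural reading is followed. For tolerated dose, unadjusted pooling raises the chance of p<0.05 from 5% to roughly 8% to 65% with no within-arm association. Mean rho stays modest, at about -0.05 to -0.21. These figures rest on an 81:41 split, the planned treatment effect (or outcome shifts of 0.5 to 0.8 SD) and assumed marker shifts of 0.5 to 3 SD.

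A reader might infer more than this, and the documents do not support it:

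- That the SAP prescribes pooling. It is silent.
- That every marker dupilumab lowers will correlate significantly. The outcome must move too, and even then significance is more likely, not assured.
- That the baseline-marker correlations share the fault. Randomization keeps baseline values unrelated to arm, apart from chance.
- That the main results are at risk. SAP 5.6.3 confines error control to the primary and first secondary endpoints, and neither uses these correlations.

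This is a worthwhile improvement to an exploratory analysis, of low severity.

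**What to change.** Add to SAP 5.11, for the change-from-baseline correlations only: Spearman's rho is reported within each treatment arm, together with a partial Spearman correlation adjusted for treatment and the randomization strata, and the p-value for association comes from the adjusted result. If a pooled unadjusted rho is also shown, label it descriptive and as including the treatment effect. The baseline-marker correlations can stay as they are.

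The cost is a sentence or two in the SAP and a BY or PARTIAL statement in the program; no new data are needed. The downside is precision. On the Fisher z scale the approximate standard error is 1/sqrt(n - 3): 0.09 for all 122 subjects, 0.11 for 81 and 0.16 for 41. The partial rho largely offsets this by using all subjects: with treatment and five degrees of freedom for the six strata it is about 1/sqrt(122 - 3 - 6) = 0.09.

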5.12. Analysis of Daily Allergy Symptom Diary Data

The daily allergy symptom diary analyses during up-dosing period will be performed on the mFAS and FAS using all observed data, respectively.

The continuous variables of the proportion of days with one or more allergy symptoms and with one or more severe allergy symptoms will be analyzed descriptively by treatment group during updosing period, separately. Similarly, the proportion of days with one or more allergy symptoms will be summarized descriptively for each symptom category defined in Section 4.5.3.

5.13. Analysis of Pediatric Eosinophilic Esophagitis Symptom Score

Listings of pediatric eosinophilic esophagitis symptom scores from parent report age 2-18 years and self-report age 8-18 years will be provided, respectively.

6. DATA CONVENTIONS

The following analysis conventions will be used in the statistical analysis.

6.1. Definition of Baseline for Efficacy/Safety Variables

Unless otherwise specified, the study baseline assessment for all measurements will be the latest available valid measurement taken prior to the first administration of study drug. If any randomized subjects are not treated, the baseline will be the last value on or prior to the randomization. In addition, maintenance period baseline is defined as the last available valid measurement taken prior to the first administration of dupilumab/placebo during the maintenance period.

The following rules specify the determination of baseline by both date/time information:

- The date and time of first injection will be used to determine the baseline for the AE, lab, PK and ADA data.
- Only the date of first injection will be used to determine the baseline for other data expect AE, lab, PK and ADA data.

For the re-screened subjects, all data from the same subject will be used to derive baseline regardless if the data is from the screen-failure subject ID or enrolled subject ID.

6.2. General Data Handling Conventions

For the laboratory safety variables and biomarker data, if the data are below the lower limit of quantification (LLOQ)/ limit of linearity, half the lower limit value (i.e., LLOQ/2) will be used for quantitative analyses. For data above the upper limit of quantification (ULOQ) / limit of linearity, the upper limit value (i.e., ULOQ) will be used for quantitative analyses.

6.3. Data Handling Convention for Missing Data

Missing data will not be imputed in listings. This section includes the methods for missing data imputation for some summary analyses, if necessary.

Adverse event

If the intensity of a TEAE is missing, it will be classified as "severe" in the frequency tables by intensity of TEAE. If the assessment of relationship of a TEAE to the investigational product is missing, it will be classified as "related" in the frequency tables by relation to the investigational product.

Adverse event start date

AE start date will be used for AE classification and analysis of AESIs. If AE start date is not complete, then the character variable will keep the original incomplete date, the numerical date variable will be imputed, and an imputation flag will indicate which date component is missing.

If AE start day is missing, and AE start month and year are not missing: If AE start year is the same as first dose year and the AE start month is the same as the first dose month, then impute AE start day using the day of first dose. If this leads to a date after the AE end date, use AE end date instead. Otherwise impute the AE start day using the first day of the month. If this leads to a date before informed consent, the informed consent date will be used. Imputation flag is 'D'.

If AE start month is missing, and AE start year is not missing: If AE start year is before the first dose year, use the informed consent day and month. If AE start year is equal to the first dose year, use the first dose day and month. If this leads to a date after the AE end date, use AE end date instead. If AE start year is after the first dose year, use 01 January. Imputation flag is 'M'.

If AE start year is missing: Impute AE start date using the date of first dose. If this leads to a date after the AE end date, use AE end date instead. Imputation flag is 'Y'.

Adverse event end date

The general recommendation is not to impute AE end date. However, since AE end date will be used for AE starting date imputation, to carry through the logic for programming, the following intermediate step will be used. Afterwards, only the original character/numeric date recorded in CRF will be kept in the final analysis dataset.

If AE end day is missing, and AE end month and year are not missing: Impute AE end date using the last day of the month. If this leads to a date after end of study follow up date, use end of follow up date instead.

If AE end month is missing, and AE end year is not missing: Impute AE end date using 31 December as the day and month. If this leads to a date after end of study follow up date, use the end of follow up date instead.

If AE end year is missing: Impute AE end date using the end of follow up date.

Prior or concomitant medication

Medication start and end date missing

To determine whether a medication is prior medication or concomitant medication or both, the missing medication start date is estimated as early as possible, and the missing medication end date is estimated as late as possible. If the medication start date is missing, the onset day will not be calculated in medication listings.

Prior medication start date

If start day is missing, and start month and year are not missing: Impute the start day using the first day of the month. Imputation flag is 'D';

If start month is missing, and start year is not missing: Impute the day and month using 01 January. Imputation flag is 'M'.

If start year is missing: Impute start date using 2 years before inform consent date. Imputation flag is 'Y'.

A special note: for start date with year missing, the general principle is not to impute. However, to simplify the programming flow, the imputation is proposed to align with the protocol which specifies to collect up to 2 years prior medication. Since the start date of prior medication will not be used in any analysis, the rule will not impact the analysis result.

Prior medication end date

If end day is missing, and end month and year are not missing: Impute end date using the last day of the month. If this leads to a date on or after first dose intake date, use first dose intake date -1 instead. Imputation flag is 'D'.

If end month is missing, and end year is not missing: Impute end date using 31 December as the day and month. If this leads to a date on or after first dose intake date, use first dose intake date -1 instead. Imputation flag is 'M'.

If end year is missing: Impute end date using the first dose intake date -1. Imputation flag is 'Y'.

Concomitant medication start date

The imputation rule for concomitant medication start date is the same as AE start date.

Concomitant medication end date

If end day is missing, and end month and year are not missing: Impute end date using the last day of the month. If this leads to a date after end of study follow up date, use end of follow up date instead. Imputation flag is 'D'.

If end month is missing, and end year is not missing: Impute end date using 31 December as the day and month. If this leads to a date after end of study follow up date, use the end of follow up date instead. Imputation flag is 'M'.

If end year is missing: Impute date using the end of follow up date. Imputation flag is 'Y'.

Medication coding

Medications whose ATC level 4 cannot be coded will be summarized by setting ATC4=ATC2 in the table programs. However, these uncoded ATC level 4 records still need to be confirmed with study DM and study MD.

PCSV

Subjects who had post-baseline PCSV but missing baseline value will be regarded as having treatment emergent PCSV.

